7.5.3 Examination of Subgroups

The primary efficacy analyses will be repeated on the ITT population based on the following subgroups:

- Gender (Male and Female)
- Race (White, Black or African American, and Other)
- Age (6-9 years and 10-12 years)

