2.4 Method of Assigning Subjects to Treatment Groups

After successfully meeting study entry criteria, subjects will be randomly assigned in a 1:1 ratio to 1 of the 2 following treatments:

- 4 mg/day dasotraline (N = approximately 55 subjects)
- Placebo (N = approximately 55 subjects)

Under previous versions of the protocol, subjects were also randomly assigned to a third treatment group in a 1:1:1 overall ratio: 6 mg/day dasotraline (N = approximately 20 subjects randomized before protocol was amended). An Interactive Response System (IXRS) will be used to manage randomization on Day 1 and, if necessary, for emergency unblinding of treatment assignment during the study. The IXRS is an integrated web based subject and drug management system.

Study medication will be assigned by an IXRS based on the randomization schedule. The IXRS will generate instructions on which medication number to assign to a subject.

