2.6 Sample Size Determination

A post-baseline least square (LS) mean of 18.66 in mean SKAMP-CS obtained from an average of 7 assessments collected across the 12-hour classroom day was observed for the placebo group in a similarly designed study (Wigal 2013) [3]. It is assumed that the dasotraline group will have approximately 20% improvement in mean SKAMP-CS

for dasotraline 4 mg/day versus placebo. The treatment mean difference in change from baseline is therefore assumed to be 4.0 units (effect size of 0.8) versus placebo on mean SKAMP-CS with a common standard deviation of 5 units for dasotraline 4 mg/day. The two-sample t-test with equal variance procedure using nQuery Version 7.0 was utilized for the sample size/power calculation. A total of 100 subjects (50 each for the dasotraline 4 mg/day and placebo groups) will provide at least 95% power to detect statistically significant treatment differences for the dasotraline dose group versus placebo in the primary endpoint at a 5% significance level (2-sided).

The study will target approximately 110 subjects randomized in an attempt to have 100 subjects complete the trial. In addition, approximately 20 other subjects were randomized to dasotraline 6 mg/day under previous versions of the protocol. The total number of subjects randomized in this study will be approximately 130.

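### SAP 7.5.3 repeats the primary test inside each gender, race and age stratum but plans no comparison of the treatment effect between strata

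*SAP*

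**What the plan says.** SAP 7.5.3 has one operative sentence, "The primary efficacy analyses will be repeated on the ITT population based on the following subgroups", followed by gender (two levels), race (three levels) and age (6-9 and 10-12 years). That makes seven strata.

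The analysis being repeated is defined in SAP 7.5.1. It is an ANCOVA of change in mean SKAMP-CS with treatment, baseline mean SKAMP-CS and site, comparing 4 mg/day with placebo at a two-sided 5% level. It reports the LS mean difference, its standard error and 95% CI, and an effect size.

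The rest of the subgroup material is brief:

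- SAP 7.5.2 adds plots of change in SKAMP-CS by age, gender and race.
- Protocol 15.3.5.5 lists the same three factors and gives no method.
- Protocol 15.3.5.4 makes no multiplicity adjustment.

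Neither document names a treatment-by-subgroup term or any other between-stratum comparison. The subgroup results are not labelled exploratory, although the SAP uses that label for the 6 mg/day arm (SAP 3 and 10).

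**The concern.** Subgroup analysis of a primary endpoint asks whether the effect is consistent across kinds of patient. Seven separate tests do not answer that. A p-value within a stratum depends on how many children are in it as well as on the effect there, so an identical effect can be significant in a large stratum and not in a small one. A table with one significant and one non-significant row invites the reading that the drug works in one group and not the other, and the plan provides no result that would check that reading. At stake is how a supportive analysis is interpreted, for example in statements about girls or about older children. The trial's main result is not at stake.

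**Working it through.** **Inputs from the documents** (SAP 2.4 and 2.6). The treatment difference is "assumed to be 4.0 units (effect size of 0.8) versus placebo", with a "common standard deviation of 5 units for dasotraline 4 mg/day". Allocation is 1:1. The sizing method is "The two-sample t-test with equal variance procedure using nQuery Version 7.0", and alpha is 0.05 two-sided. The stated result is: "A total of 100 subjects (50 each for the dasotraline 4 mg/day and placebo groups) will provide at least 95% power".

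**Assumed.** The documents give no subgroup sizes, so I use a range of splits of 50 per arm, with arms balanced within each stratum.

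**1. The plan's own figure.** Noncentral t with d = 4.0/5 = 0.8, n = 50 per arm, df = 98 and noncentrality 0.8 × √(50/2) = 4.0 gives power of 97.7%. This meets the stated floor of 95%.

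**2. Two-level factors, same true effect (4 units) in both strata.** Within a stratum of n per arm, the noncentrality is 0.8 × √(n/2) with df = 2n − 2. The strata contain different children, so the separate tests are independent and

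P(disagree) = pA(1 − pB) + pB(1 − pA).

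| Per-arm split | Power, larger or equal stratum | Power, other stratum | P(disagree) |
|---|---|---|---|
| 25/25 | 79.1% | 79.1% | 33% |
| 30/20 | 86.1% | 69.3% | 36% |
| 33/17 | 89.3% | 61.9% | 41% |
| 38/12 | 93.1% | 46.6% | 53% |
| 40/10 | 94.2% | 39.5% | 59% |

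Example, 40/10: 0.942 × 0.605 + 0.395 × 0.058 = 0.570 + 0.023 = 0.593.

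**3. Race, three levels.** P(mixed) = 1 − P(all significant) − P(none significant). For 17/17/16 per arm the powers are 0.619, 0.619 and 0.591. All are significant with probability 0.226 and none with probability 0.060, so results are mixed in 71% of trials. For 30/15/5 the figure is 85%.

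**4. Sensitivity to the effect and SD.**

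- Taking 20% of 18.66 without rounding (3.73 units), disagreement is 39% at 25/25 and 62% at 40/10.
- With a true effect of 3 units it is 50% and 63%.
- With a residual SD of 4 instead of 5 (effect size 1.0) it is 12% and 44%, and 48% for race at 17/17/16.

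**5. What an interaction term would give.** A 5% interaction test signals a false difference in 5% of trials per factor, by construction. For two levels, SE = 5 × √(2/nA + 2/nB), with n per arm. Power below is for a true between-stratum difference of 4 units, Φ(4/SE − 1.96).

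| Per-arm split | SE | 95% CI half-width (1.96 × SE) | Power for a 4-unit difference |
|---|---|---|---|
| 25/25 | 2.0 | 3.9 | 52% |
| 33/17 | 2.1 | 4.1 | 47% |
| 38/12 | 2.3 | 4.6 | 40% |
| 40/10 | 2.5 | 4.9 | 36% |

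**The case against.** The strongest reply is that the plan does not commit the error. A reader might infer from the repeated 5% test that subgroup effects will be judged present or absent by significance. No passage says so, and no objective or endpoint concerns a subgroup. The harm needs a later misreading.

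A reader might also infer that the plan leaves no valid way to compare strata. That is too strong. The repeated analysis gives a difference, SE and 95% CI per stratum, and for two separate strata the contrast can be derived as the difference of the estimates with SE = √(SE₁² + SE₂²). SAP 1 places table specifications in separate documents, so how p-values will be displayed is unknown. All of this stands. What remains is that the contrast is not planned and no rule for reading the strata is given.

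The size of the effect can also be challenged. Quoting only uneven splits would exaggerate it, since age could divide nearly evenly. That is why the 33% figure belongs beside the 59%. The t-test with SD 5 ignores covariate adjustment. If SD 5 is not already net of baseline and site, disagreement would be lower, as step 4 shows, while degrees of freedom spent on site in small strata work the other way.

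It is tempting to add that site effects will be poorly estimated in small strata. SAP 7.1.2 expects up to five sites with at least 12 subjects each, but the documents give no stratum sizes. Site is a nuisance term, and imprecision in its coefficients does not by itself bias the treatment contrast. I do not rely on this argument.

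Finally, the interaction would often be uninformative. That is correct, and it is a reason to report the interval and not the p-value alone.

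**Conclusion.** The point holds as a limited gap in a supportive analysis. SAP 7.5.3 produces seven within-stratum tests and no planned between-stratum comparison, so its p-values cannot show whether the effect differs. Under the sponsor's planning values and an identical true effect, contradictory significance would be common: about one trial in three for an evenly split two-level factor, 59% at 40/10 per arm, and about 71% for three near-equal race groups. These figures rest on assumed subgroup shares, a true effect of 4 units and SD 5. The documents do not support the stronger reading that the sponsor intends to judge subgroups by significance, or that per-stratum estimates are missing. The primary conclusion, alpha and sample size do not change.

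**What to change.** In SAP 7.5.3, for each factor, add one ANCOVA on the ITT subjects randomized to 4 mg/day or placebo, using the primary model plus subgroup and treatment-by-subgroup terms. Report the interaction estimate with its 95% CI (for race, a joint test across the three levels) beside the within-subgroup differences and their CIs. Label the subgroup analyses exploratory, and state that no differential effect will be claimed from within-stratum p-values.

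The cost is a few lines of text and a little programming, with no new data. The drawback is imprecision: a half-width of about 4 to 5 units is as large as the whole assumed effect. The interaction must therefore be read through its interval, and a non-significant interaction must not be presented as proof of consistency.

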8. SAFETY EVALUATION

All safety analyses will be performed on the safety population, which includes subjects who had been treated with dasotraline 6 mg/day under the first version of the protocol. All subjects who were randomized and received at least 1 dose of study medication will be assessed for safety. Safety will be monitored by physical and neurological examinations, vital signs, AEs assessed at each visit, electrocardiography, and clinical laboratory tests. In addition, the C-SSRS will be administered at Screening (Visit 1) and all subsequently scheduled visits to assess emergent suicidal thoughts or behaviors.

8.1 Overview of Safety Analysis Issues

Missing end dates for AEs will not be imputed. If end date information is not available, it will be assumed that the finding or event is ongoing.

Missing AE start dates will be imputed based on the following rules:

- If only the year is known, the date will be set to 01 January of that year. If the year is the same as the year of the first dose of study medication, the date will be set to the date of the first dose of study medication.
- If the year and day are known, the date will be set to January of that year. If the year and day is the same as the year and day of the first dose of study medication, the date will be set to the date of the first dose of study medication.
- If the year and month are known, the date will be set to first day of the month. If the year and month are the same as the year and month of the first dose of study medication, the date will be set to the date of the first dose of study medication.
- If the start date is completely missing, it will be set to the date of the first dose of study medication.

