15.3.6.1. Adverse Events

All AEs will be coded using Medical Dictionary for Regulatory Activities (MedDRA) version 18.0 or higher. AEs are untoward medical occurrences:

- that occurred on or after the first dose of study medication,
- with a missing start date and a stop date on or after the first dose of study medication, or
- with both a missing start and stop date.

AEs will be summarized by treatment and by MedDRA system organ class (SOC) and Preferred Term (PT).

The following AEs will be summarized and presented by treatment group and by MedDRA SOC and PT for the Safety population:

- All AEs (including number of events and subject incidence).
- Serious AEs.
- AEs leading to discontinuation.
- AEs by maximum severity (mild, moderate, severe).
- AEs by relationship to the study treatment (related, or not related).
- Serious AEs by relationship to the study treatment.
- AEs leading to death.

The following conventions will be followed in summarizing AEs:

- For subject incidence summaries, each subject will be counted only once within each SOC and within each preferred term.

- If a subject reports more than one AE within a preferred term and/or a body system, the AE with the highest known severity within each body system and within each preferred term will be included in the summaries by severity.
- For summaries by relationship to the study medication, AEs will be grouped as “related” or “not related.” AEs assessed as “possible,” “probable,” or “definite,” will be grouped as “related.” If a subject reports more than one AE within the same treatment regimen, SOC and PT, and any are related, it will be summarized as related. AEs whose relationship to treatment is assessed as “not related” or “unlikely” will be grouped as “not related.”

A listing of AEs, as well as a listing of deaths, SAEs, or AEs leading to discontinuation, will be presented.

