8.4 Adverse Events

All AEs will be coded using MedDRA Version 19.0. An AE is any untoward medical occurrence:

- that occurred before, on or after the first dose of study medication,
- with a missing start date and a stop date before, on or after the first dose of study medication, or
- with both a missing start and stop date.

Untoward medical occurrences that occur between the time of informed consent/assent and first study drug administration are pre-treatment events. Those that occur after first administration of study drug are considered AEs. Clinically significant abnormal objective findings (eg, clinical laboratory value, ECG value, and physical examination observation) will also be recorded as AEs.

A serious adverse event (SAE) is an AE that meets one or more of the following criteria:

- Results in death.
- Is life threatening.
- Requires hospitalization or prolongation of existing hospitalization.
- Results in persistent or significant disability or incapacity.
- Is a congenital anomaly or birth defect.
- Is an important medical event that may jeopardize the subject or may require a medical or surgical intervention to prevent one of the outcomes listed

above. Examples of such medical events include allergic bronchospasm requiring intensive treatment in an emergency room or at home, blood dyscrasias or convulsions that do not result in inpatient hospitalization.

An AE is considered treatment emergent if it started during or after administration of the first dose of study medication. In addition, medical history events that worsen in severity after the start of dosing will be considered treatment-emergent adverse events (TEAEs). If a subject discontinues early from the study and has an AE after his/her last dosing date, the AE will be deemed as treatment emergent if it occurs ≤ 72 hours after the last dose and not as treatment emergent if it occurs >72 hours after the last dose of study medication. AEs with partial start dates will be imputed as outlined in Section 8.1 and assigned to the associated treatment period.

Summary Tabulations

An overview of the frequency, i.e., the number and percentage of subjects and events with at least one of the following AEs, will be presented by treatment group (placebo, dasotraline 4 mg/day, dasotraline 6 mg/day, and combined dasotraline [4 mg/day + 6 mg/day]):

- All TEAEs
- SAEs
- TEAEs leading to discontinuation
- Severe TEAEs
- TEAEs related to study medication
- Severe TEAEs

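### An on-treatment adverse event recorded with day and year but no month can be dated to a January before the first dose and so drop out of the TEAE tables

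*SAP*

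**What the plan says.** SAP 8.1 has four bullets for incomplete AE start dates.

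- **Year only.** The default is 1 January, but with a broad fallback: "If the year is the same as the year of the first dose of study medication", the event takes the first-dose date.
- **Year and day, no month.** "If the year and day are known, the date will be set to January of that year". The fallback here is narrow. It opens "If the year and day is the same as the year and day of the first dose of study medication", and only then does the event take the first-dose date.
- **Year and month, no day.** The first of that month, or the first-dose date if year and month match the first dose.
- **Nothing known.** "If the start date is completely missing, it will be set to the date of the first dose of study medication".

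SAP 8.4 makes the resulting date decisive. It states: "An AE is considered treatment emergent if it started during or after administration of the first dose of study medication". It also states: "AEs with partial start dates will be imputed as outlined in Section 8.1 and assigned to the associated treatment period". Neither section compares the imputed date with the stop date, the consent date or the last visit.

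**The concern.** Three of the four bullets lean toward calling an ambiguous event treatment-emergent. The missing-month bullet leans the other way for almost every same-year event, so a record that holds more information (day and year) is treated less cautiously than one that holds less (year alone).

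What is at stake is every table labelled TEAE in SAP 8.4: overall incidence, maximum severity, relationship to study drug, and discontinuation. Overall AE incidence is a secondary endpoint in Protocol 6.2, and the arms are small.

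**Working it through.** The documents give no figure on this point, so there is none to reproduce. The check applies the four bullets literally.

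**Inputs.** The imputation bullets are in SAP 8.1, the TEAE definition in SAP 8.4 and the study-day formula in SAP 3. Protocol 7.1 limits screening to 35 days before the first dose. Protocol 12.1.1 collects AEs from the first dose to the last visit, which is Day 21 ± 2 (Protocol 11.5.3). Calendar dates of dosing are not given, so all months are shown.

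**Step 1: one event under four records.** First dose 10 June; event starts 20 June of the same year.

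| What is recorded | Imputed start | TEAE? |
|---|---|---|
| Year only | 10 June | yes |
| Day 20 and year | 20 January | no |
| June and year | 10 June | yes |
| Nothing | 10 June | yes |

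In a non-leap year 10 June is day 161, so 20 January is study day 20 − 161 = −141. Screening reaches back 35 days at most, so the imputed date cannot be true under the trial's own schedule.

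**Step 2: share of on-treatment events lost, given this date pattern.** Let W be the window in days from Day 1: 15 (second classroom day), 21 (nominal last visit) or 23 (latest last visit). Assume onset is uniform over the window and first doses are uniform over the month. No day of the month repeats within 23 days, so the matching-day exception saves only Day 1.

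- *First dose February to November.* Every window ends in the same year, so the loss is (W − 1)/W: 14/15 = 93.3%, 20/21 = 95.2%, 22/23 = 95.7%.
- *First dose on day d of December.* Events in the following January carry the new year and are dated correctly. The loss is min(W, 32 − d) − 1 of W days. Summed over d = 1 to 31: 329/465 = 70.8%, 410/651 = 63.0%, 429/713 = 60.2%.
- *First dose on day d of January.* January events are dated correctly; those in February are moved back before the dose. The loss is W − min(W, 32 − d) of W days: 105/465 = 22.6%, 210/651 = 32.3%, 253/713 = 35.5%.
- *The other three bullets.* 0% in every month.

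**Step 3: edge cases.**

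| First dose | True start | Imputed | Result |
|---|---|---|---|
| 10 June | 10 June | 10 June | kept by the exception |
| 20 December | 3 January, next year | 3 January, next year | correct |
| 25 January | 3 February | 3 January | lost |
| 10 June | 10 May (screening) | 10 June | pre-treatment event counted as a TEAE |

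The last case is possible because 10 May is 31 days before 10 June, inside the 35-day screening period.

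**Step 4: effect of one event.** With about 55 children per main arm, one child is 1/55 = 1.8 percentage points. With about 20 on 6 mg/day it is 1/20 = 5 points. This applies only if the lost event was the child's only one in that category.

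**The case against.** The strongest objection is rarity. A known day and year with an unknown month is an odd pattern in a child followed for about three weeks, with AEs recorded on Day 15 and at the final visit. Queries run through the data-capture system (Protocol 16.1), and SAP 4 requires data issues to be resolved before lock. A start date before consent is easy to query. This stands: it lowers the expected count, but the rule still gives the wrong date whenever it is used.

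Four stronger readings are tempting, and the documents do not support them.

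- *Every child dosed after January loses such events.* No: the matching-day exception and the January after a December first dose both keep events, while some children dosed in January lose theirs.
- *The error always under-counts.* No: the 10 May example in step 3 over-counts.
- *The event disappears from the safety report.* No: SAP 8.4 lists all AEs by subject, and its SAE and death tables are not labelled treatment-emergent. The listing of AEs leading to discontinuation follows the case report form. Only the TEAE-labelled tables are sure to lose the event.
- *The SAP contradicts the protocol.* Protocol 15.3.6.1 counts an event "with a missing start date and a stop date on or after the first dose of study medication", but it does not say that a partial date is a missing one. The last bullet of SAP 8.1 already handles a wholly missing start. The comparison shows that the stop date is useful information that SAP 8.1 ignores; it does not show a contradiction.

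**Conclusion.** The concern holds within limits. An on-treatment event with day and year but no month, in the same year as the first dose and on a different day of the month, is dated before the first dose if that dose was after January. Events in February after a January first dose fare the same. SAP 8.4 then excludes them from the TEAE tables, although the year-only bullet would have kept them.

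Given the date pattern, the loss is 93.3% to 95.7% for February to November first doses, 60.2% to 70.8% for December and 22.6% to 35.5% for January. These shares rest on uniform onset and dosing dates. They are not shares of all AEs: the documents give no frequency for the pattern, and the absolute number is probably small. The primary efficacy analysis is unaffected. The bullet should still be changed before unblinding, because following the plan exactly gives a wrong classification and the correction is simple.

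**What to change.** Replace the second bullet of SAP 8.1 with:

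> If the year and day are known but the month is missing: if the year is the same as the year of the first dose, set the start to the first-dose date, unless the recorded stop date is before the first dose, in which case the event is pre-treatment; otherwise use that day in January of the recorded year.

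This extends the year-only fallback. Under the step 2 assumptions it loses 0% of on-treatment events in every dosing month.

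If the known day is to be used, consider the months of that year that place the date between consent and the end of AE or SAE collection, and not after the stop date.

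- Take the earliest such date on or after the first dose.
- If all such dates precede the first dose, keep the event as pre-treatment.
- If no date fits, use the first-dose date unless the stop date precedes it.

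The second condition is needed. With consent on 6 May, first dose on 10 June, last visit on 2 July and a non-serious event on day 7, the only candidates are 7 May and 7 June. Both precede dosing, so the event must not default to 10 June.

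The cost is one SAP bullet and a small change to the AE date program. The downside is that a few pre-treatment events may be counted as TEAEs, as the other bullets in SAP 8.1 already accept.

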15.3.7. Treatment of Missing Data

Missing data handling for efficacy endpoints will be detailed in the statistical analysis plan (SAP). No missing data handling will be applied for safety endpoints.

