12.2 Changes in the Analysis Planned in the Protocol

No changes are planned as of the date of the SAP.

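### SAP 8.1 can move an adverse event that ended before any drug onto the first-dose date, because its start-date imputation never reads the stop date

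*SAP*

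**What the plan says.** **SAP 8.1** gives rules for incomplete adverse event start dates:

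- Start completely missing: "If the start date is completely missing, it will be set to the date of the first dose of study medication".
- Only the year known: "If the year is the same as the year of the first dose of study medication, the date will be set to the date"; the date meant is that of the first dose.
- Year and month known: "If the year and month are the same as the year and month of the first dose of study medication, the date will be set"; the target is again the first-dose date. The year-and-day rule works in the same way.
- If the known parts do not match the first dose, the missing parts default to January or to the first of the month.

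End dates appear in this section only to say that "Missing end dates for AEs will not be imputed" and that an event without one is taken as ongoing. No rule compares the start with a recorded end.

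**SAP 8.4** uses the result: "AEs with partial start dates will be imputed as outlined in Section 8.1 and assigned to the associated treatment period". An event is treatment-emergent if it began at or after the first dose. The section's definition of an adverse event also admits one with a missing start and a stop on either side of the first dose. A separate sentence there says that occurrences between consent and first dose are pre-treatment events. Protocol 12.1.1 says the same.

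**Protocol 15.3.6.1** is narrower. It admits an event that occurred on or after first dose, one "with a missing start date and a stop date on or after the first dose of study medication, or" one with both dates missing. **SAP 12.2** states: "No changes are planned as of the date of the SAP".

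**The concern.** A recorded stop date before the first dose settles the matter: the event cannot have begun on treatment, however incomplete its start date. The SAP discards that information and gives the event an onset later than its own end.

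Occurrences are collected from consent, up to 35 days before first dose, and every child stops methylphenidate 3 to 5 days before Day -1. Short-lived symptoms that resolve before dosing are therefore plausible. If such an event is moved to Day 1, it is tabulated as treatment-emergent on dasotraline or placebo and appears in listings with an impossible pair of dates. Adverse event incidence is a listed endpoint, and safety is a secondary objective.

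**Working it through.** The plan states no figure on this point, so there is none to reproduce. The check is a trace of the rules and a count of how far they reach.

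**1. Worked example (assumed dates).** First dose 20 September; recorded stop 10 September of the same year.

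| Start as recorded | Start under SAP 8.1 | SAP 8.4 | Protocol 15.3.6.1 |
|---|---|---|---|
| Day unknown, September known | 20 September | treatment-emergent | not an adverse event |
| Only the year known | 20 September | treatment-emergent | not an adverse event |
| Completely missing | 20 September | treatment-emergent | not an adverse event |

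Duration by the formula in SAP section 3 (end minus start plus 1): 10 - 20 + 1 = -9 days.

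**2. Where the conflict is direct and where it is inferred.** The third row contradicts protocol 15.3.6.1 outright, as does the SAP 8.4 definition that admits a pre-dose stop. For the first two rows the protocol's stop-date rule does not name partial dates, so one further step is needed. SAP 8.1 lists partial dates under its heading for missing start dates, and an event that ended before first dose cannot meet the protocol's other criterion of having occurred on or after first dose. All three rows also conflict with the pre-treatment definition in protocol 12.1.1 and SAP 8.4.

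**3. How far the matching rules reach.** Assume first-dose dates spread evenly over a year.

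- Day unknown: a start k days before first dose (k up to 28) falls in the same month for a share 1 - 12k/366 of first-dose dates. At k = 1 this is 0.967, at k = 5 it is 0.836, at k = 14 it is 0.541. The mean over k = 1 to 6, the withdrawal window, is 1 - 12 x 3.5/366 = 0.885.
- Day unknown, whole window (365-day year, one-day events spread evenly over the days before dosing): for 8 days, 1 - 12 x 4.5/365 = 0.852. For the full 35 days, direct enumeration gives 0.421.
- Only the year known: 1 - 4.5/365 = 0.988 for 8 days and 1 - 18/365 = 0.951 for 35 days.

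These shares apply only to events that already have the relevant part of the start date missing. The defect needs a recorded pre-dose stop as well.

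**4. Size per event.** One child moved adds 1/55 = 1.8 percentage points to an arm's incidence for that term, using the planned 55 per arm.

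**5. The corrected rule on the same example.** If the stop date is read first, 10 September precedes 20 September, so the event is pre-treatment in all three rows. This agrees with the protocol.

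**The case against.** **Pre-treatment events are a separate category.** The protocol collects them from consent and starts adverse event recording after the first dose; the schedule marks adverse event monitoring only at Day 15 and end of study. On one reading, an event known to be over before dosing is already pre-treatment and never reaches SAP 8.1. This has weight: the documents do not show whether the case report form separates the two categories, so misclassification is possible rather than certain. But nothing in the SAP secures that reading. The SAP 8.4 definition takes in occurrences before first dose, including those with a missing start and a pre-dose stop, and no date rule screens them out before imputation.

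**Imputing to first dose is conservative.** That is true where the stop date is missing or on or after first dose, and it should stay there. With a recorded pre-dose stop there is no doubt for the rule to resolve.

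**Protocol 15.3.7.** It says "No missing data handling will be applied for safety endpoints", and a reader might infer that all date imputation in the SAP is an undeclared departure. The documents do not support that. Protocol 15.3.6.1 itself contains a convention for missing dates, so 15.3.7 cannot sensibly forbid such conventions.

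**SAP 5.1.** A reader might say that the SAP already does better for medications. It does use the available information for partial dates, but it treats a completely missing start as both prior and concomitant whatever the stop date. Its practice is mixed and proves little.

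**Consequence.** Safety is summarised descriptively, the rule is the same in both arms, and neither the primary endpoint nor any formal test depends on it. This stands in full.

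**Conclusion.** The rule is wrong as written. SAP 8.1 with SAP 8.4 can class an event recorded as ending before any drug as treatment-emergent, contrary to protocol 15.3.6.1 and to the pre-treatment definition in both documents, with no change declared in SAP 12.2. The firmest ground is the rule for a completely missing start together with the widened SAP 8.4 definition; the partial-date rules follow by a short inference.

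The effect is limited to descriptive adverse event tables and listings. It is probably small, and it cannot be quantified without the number of incompletely dated events that have a recorded pre-dose stop. A reader might infer that almost every undated withdrawal symptom is moved to Day 1. The supportable figures are about 88% for starts 1 to 6 days before dosing with only the day missing, and about 42% over the 35-day window, both on the even-spread assumptions above. Neither measures impact on the tables. An event dated to an earlier month, with the month recorded, stays pre-treatment.

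**What to change.** - In SAP 8.1, put a condition ahead of the imputation rules: the start is set to the first-dose date only if the stop date is missing or is on or after first dose. Otherwise the event is pre-treatment and its start is not moved to first dose.
- Add that an imputed start may never be later than a known stop. Where the stop is itself partial, treat the event as pre-treatment only if the known parts place the stop wholly before first dose.
- Align the adverse event definition in SAP 8.4 with protocol 15.3.6.1 by removing the admission of a pre-dose stop.

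There is no need to list the remaining date imputation as a departure from protocol 15.3.7. The cost is a sentence or two in SAP 8.1, an edit to the SAP 8.4 definition and one condition in the adverse event derivation program. No new data are required.
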